A Multi-center Clinical Study on the Efficacy and Safety of Kuntai Capsule Alone and in Combination With Hormones in the Treatment of Early-onset Hypoovarian Function

NCT05021094

Date: August 4, 2021

Research Proposal Summary

| Scheme number | HYKT18017S |
|------------------------|---|
| Scheme name | A Multi-center Clinical Study on the Efficacy and Safety of Kuntai Capsule Alone and in |
| | Combination With Hormones in the Treatment of Early-onset Hypoovarian Function |
| Version number/date | Version 2.1 , June 18 , 2021 |
| sponsor | Shanghai Haitian Pharmaceutical Technology Development Co., Ltd. |
| Clinical trial staging | Post-marketing clinical re-evaluation |
| test drug | Heyan Kuntai Capsules [®] (Z20000083), each0.5g, was produced by Guiyang Xintian Pharmaceutical Co., Ltd. |
| Indications | POI (including subclinical stage) |
| Test purposes | To evaluate [®] the efficacy and safety of Heyan Kuntai Capsules alone or in combination with hormone therapy in patients with POI (including subclinical stage) in improving ovarian function . |
| Research design | Prospective, multicenter, randomized, controlled clinical trial design |
| total number | It is planned to complete 120 cases (considering the 20% dropout rate, at least 150 cases need to be |
| of cases | enrolled) |
| number of research | 6_ |

| centers | |
|--------------|---|
| Study period | 24 months |
| research | Diagnostic criteria : |
| object | The diagnostic criteria for premature ovarian insufficiency (POI) refer to the "2017 Chinese |
| | Expert Consensus on Clinical Diagnosis and Treatment of Premature Ovarian Insufficiency" and |
| | "2016 Expert Consensus on Hormone Supplementation Therapy for Premature Ovarian |
| | Insufficiency"; including: (1) Age <40 years old; (2) oligomenorrhea or amenorrhea for at least 4 |
| | months; (3) at least 2 times serum basal follicle-stimulating hormone (FSH) > 25 IU/L (interval > 4 |
| | weeks). Subclinical POI: FSH level is 15~25 IU/L, which is a high-risk group. |
| | The diagnostic criteria for premature ovarian failure (POF) refer to the "2017 Chinese Expert |
| | Consensus on Clinical Diagnosis and Treatment of Premature Ovarian Insufficiency", which refers |
| | to amenorrhea, FSH>40IU/L, and decreased estrogen levels before the age of 40, accompanied by |
| | varying degrees of perimenopause Stage symptoms are the terminal stage of POI. |
| | standard constrain: |
| | 1. 18 years old ≤ age < 40 years old; |

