| | 2. At least two (>4 weeks interval) basal FSH≥15IU/L, with or without oligomenorrhea or |
| | menopause. |
| | 3. Informed consent, voluntary experiment. |
| | Exclusion criteria: |
| | 1. pregnant and lactating patients; |
| | 2. Patients with endometriosis , adenomyosis , endometrial lesions (submucosal fibroids , |
| | endometrial polyps, etc.), uterine fibroids >4cm or hysterectomy; |
| | 3. Patients with known or suspected history of breast cancer and estrogen-dependent |
| | malignancies; |
| | 4. a personal history of venous thromboembolism (VTE) or with a high risk of VTE (including |
| | body mass index > 30 kg/m ² , smoking, family history of thrombophilia); |
| | 5. Porphyria patients; |
| | 6. Patients with serious primary diseases such as cardiovascular, liver, kidney, hematopoietic |
| | system or mental illness; |

- 7. Patients who are participating in other clinical trials or have participated in other clinical trials within the past three months;
- 8. Patients with suspected or real history of alcohol and drug abuse;
- 9. Known allergy to the investigational drug or its components;
- 10. Other patients deemed unsuitable for participation in this trial by the investigator.

Note: Patients who were receiving hormone replacement therapy at the time of recruitment were required to take at least a 3 -month suspension of medication to participate in this trial.

Trial grouping

and medication

1 POI patient

According to the random sequence generated by computer, eligible patients were randomly assigned to Kuntai group, control group and combination group according to 1:1:1.

- (A) Kuntai group (30 cases): Oral Kuntai capsules, 4 capsules at a time, 3 times a day, 28 days as a course of treatment, taking medicine for 3 courses;
- (B) Control group (30 cases): the sequential regimen of estrogen and progesterone was used, and the drug was estradiol tablets/estradiol dydrogesterone tablets (fenmetone), and red tablets (estradiol, 2 mg/d), and gray tablets (estradiol, 2 mg/d, dydrogesterone, 10 mg/d) were taken for the next 14 days, 28 days as a course of treatment, and three courses of medication were taken.
- (C) Combination group (30 cases): On the basis of hormone therapy, Kuntai Capsules were added, and the dose was the same as that of Kuntai group and hormone group for 3 months.

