- 2. Patients with POI in subclinical stage: self-control before and after experiment group (30 cases): Oral Kuntai capsules, 4 capsules at a time, 3 times a day, 28 days as a course of treatment, taking medicine for 3 courses of treatment.

Treatment and

follow-up

- 1. Course of treatment: 28 days as a course of treatment, taking medicine for 3 courses of treatment
- 2. Visit points: before treatment (stage V $_{0}$, screening period, days -35 $\rm to~0$), baseline period (day
- 0), after 3 months of treatment (stage V_1 , days 84 to 105), drug withdrawal 3 months later (V_2 stage, 168-210 days) and 6 months after drug withdrawal (V_3 stage, 252-315 days).

Specific inspection items include:

- 1. The patient 's hormone levels (basal FSH, LH, E₂) were detected in V₀, V₁, and V₂ stages;
- 2 Anti-Müllerian hormone (AMH) was detected in patients at V 0 and V 1 stages;
- 3 The patients underwent B-ultrasound at V 0 and V 1 stage to monitor the follicular development,

| | record the number of antral follicles (AFC), ovarian hemodynamic parameters (PSV, EDV, S/D, RI |
|----------------|---|
| | and PI); |
| | 4. Modified Kupperman score was performed in V $_{0}$, V $_{1}$ and V $_{2}$ stage; |
| | 5 Pregnancy was recorded at the V $_2$ outpatient follow-up for patients with reproductive needs; |
| | 6 patients at V $_{0}$ and V $_{1}$ to detect blood routine (RBC, WBC, PLT, HGB) , liver function (ALT, |
| | AST) and renal function (BUN, Cr), and recorded adverse events. |
| | |
| | Note: |
| | 1 Basal follicle-stimulating hormone (FSH) \geq 15IU/L at first visit in patient V0, and if other |
| | inclusion criteria are met, if the patient has a history of testing with a baseline FSH ≥ 15 IU/L in |
| | the past (interval> 4 weeks), he or she can be included in this study and drug therapy can be |
| | started; (Interval > 4 weeks) If the basic FSH \geq 15 IU/L has not been diagnosed, the patient is |
| | required to visit the hospital again after 4 weeks. If the basic FSH is still \geq 15 IU/L, they can be |
| | included in this study and drug therapy can be started. |
| | 2 For patients with regular menstrual periods, the basal FSH and antral follicle count (AFC) |
| | should be followed up on the 2nd to 4th day of the menstrual cycle. If the patient has menstrual |
| | cramps after the follow-up and has not exceeded the visit window, they are required to re-examine |
| | on the 2nd to 4th day of the menstrual cycle and record the examination data. |

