A Multi-center Clinical Study on the Efficacy and Safety of Kuntai Capsule Alone and in Combination With Hormones in the Treatment of Early-onset Hypoovarian Function

NCT05021094

Date : August 4 , 2021

Statistical analysis

The case observation form completed by the test center was reviewed and returned by the project team of Shanghai Haitian Pharmaceutical Technology Development Co., Ltd., and the data was processed by a statistical analyst. The data in the case report form is entered in two copies, and the database is locked after verification and confirmation. SPSS26.0 software was used for statistical analysis. The full analysis set (FAS) and the per-protocol set (PPS) were used for effectiveness analysis, and the safety data set (SS) was used for safety analysis. Measurement data were expressed as mean \pm standard deviation ($\bar{x} \pm s$), multiple time points were compared by repeated measures analysis of variance, and pairwise comparisons were by Bonferroni test; enumeration data were expressed by the number of cases or percentages, and χ^2 was used.Test for statistical comparison.P<0.05 indicated that the difference was statistically significant.

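### Repeated-measures ANOVA with no missing-data rule would make the FAS analysis of FSH and Kupperman score largely a completers' analysis at the planned 20% dropout

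*SAP*

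**What the plan says.** The protocol (study endpoint) names FSH and modified Kupperman score as primary. Both are measured at V0, V1 and V2 (Treatment and follow-up, inspection items 1 and 4). V1 is "after 3 months of treatment (stage V_1 , days 84 to 105"; V2 is days 168–210. No efficacy visit falls between day 0 and V1.

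On numbers, the protocol summary says "It is planned to complete 120 cases (considering the 20% dropout rate, at least 150 cases need to be" enrolled. Women with POI are "randomly assigned to Kuntai group, control group and combination group according to 1:1:1", with 30 planned per arm. The subclinical cohort is a single uncontrolled group, "self-control before and after experiment group (30 cases").

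The SAP is one paragraph. It says "The full analysis set (FAS) and the per-protocol set (PPS) were used for effectiveness analysis" and defines neither set. For repeated measurements it says "multiple time points were compared by repeated measures analysis of variance, and pairwise comparisons were by Bonferroni test", in SPSS 26.0 with no procedure named. It mentions no imputation, mixed model or missing-data sensitivity analysis. Neither document says whether women who stop the study drug are still asked to attend V1 and V2.

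**The concern.** Classical repeated-measures ANOVA works on one complete set of visits per woman. A woman with V0 and V1 but no V2 is left out altogether, and her V1 value goes with her. V1 is the end-of-treatment measurement, so this discards a key result that has already been collected.

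With one woman in five expected to leave, an analysis labelled FAS would rest mostly on women who completed. If those who leave are the ones who responded poorly, the remaining women look better than the group that started. The subclinical cohort has no comparator to absorb this, so its before-after change is the most directly exposed. Between the randomised arms, the risk depends on whether women leave for different reasons or at different rates. That is plausible, because the regimens are capsules, hormone tablets or both, and the documents describe no blinding.

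**Working it through.** **1. The plan's own figure.** 120 / (1 − 0.20) = 150, as stated. The base is 4 groups × 30 = 120. So 150 − 120 = 30 women are expected to lack complete data, if all dropout falls before V2. The protocol gives no timing, and visits run to V3 (days 252–315), so 30 is an upper figure.

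**2. Information lost.** Take 30 / 0.8 = 37.5, rounded up to 38 enrolled per arm, with all loss after V1. The standard error of a V1 arm difference, in SD units, is √(2/38) = 0.23 with every V1 value and √(2/30) = 0.26 with completers only. This cost arises whatever the reason for dropout.

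**3. Bias in within-group change.** The documents give no SD, correlation or dropout mechanism. The assumptions are: outcome SD 1, lower is better, equal correlation ρ between visits, 20% lost after V1, and log-odds of dropout rising with poor response at slope 0.5, 1 or 2 per SD.

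*Dropout follows the V1 level.* At ρ = 0.6 the completers' raw means shift by 0.10, 0.17 and 0.26 SD at V1, and by 0.06, 0.10 and 0.16 SD at V2. Completers' V0 shifts by ρ times the V1 shift, exactly as V2 does. Hence:
- V1 change: bias = (1 − ρ) × V1 shift = 0.4 × (0.10, 0.17, 0.26) = 0.04, 0.07, 0.10 SD. Direct simulation gives 0.04, 0.07 and 0.10 to 0.11.
- V2 change: the V0 and V2 shifts cancel, so bias = 0.

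*Dropout follows the V1 change from baseline.* With ρ equal throughout, the regression of the V2 change on the V1 change has slope (1 − ρ) / [2(1 − ρ)] = 1/2. The V2 bias is therefore half the V1 bias. Large-sample simulation (2,000,000 women per arm, true change −0.80 SD, slope per SD of the outcome) gives this overstatement of improvement in completers:

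| ρ | V1, slopes 0.5 / 1 / 2 | V2, slopes 0.5 / 1 / 2 |
|---|---|---|
| 0.4 | 0.12 / 0.20 / 0.30 | 0.06 / 0.10 / 0.15 |
| 0.6 | 0.08 / 0.14 / 0.22 | 0.04 / 0.07 / 0.11 |
| 0.8 | 0.04 / 0.08 / 0.13 | 0.02 / 0.04 / 0.06 |

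The SD of the change at ρ = 0.6 is √(2 × 0.4) = 0.89. Counting the slope per SD of the change moves the ρ = 0.6 row to about 0.09–0.23 at V1 and 0.04–0.12 at V2. With slope 0 the bias is zero. A likelihood estimate using all observed visits returns −0.80 in every row.

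**4. Bias in the randomised contrast.** V2 change, true difference −0.50 SD, ρ = 0.6, slope 1 per outcome SD:

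| Dropout | Completers | Likelihood, all visits |
|---|---|---|
| 20% in each arm, same link to response | −0.50 | −0.50 |
| One common rule, 16% vs 24% lost | −0.48 | −0.50 |
| 10% vs 30% lost | −0.43 | −0.50 |

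With no true difference and 37 per arm, the type I error of the completers' test is 5.2% at 20% in each arm (slope 1). At 10% vs 30% it is 5.9% (slope 1) and 7.1% (slope 2).

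**5. Loss before V1.** If the same poor responders leave before V1, their response is never seen. At ρ = 0.6 and slope 1, the V2 change is −0.872 in completers and −0.845 from a mixed model that keeps their baselines, against a true −0.80. The model removes 0.027 of the 0.072 bias.

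**The case against.** Several points on the other side stand.

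- **Deletion is inferred.** The SAP does not say that incomplete cases are dropped. It follows from the named method when nothing else is specified; an undocumented imputation would change it.
- **Bias is not general.** A reader might infer that the arm comparison is biased whenever dropout follows poor response. The documents do not support that. With equal dropout and the same link to response, the completers' contrast is unbiased (step 4).
- **Raw visit means overstate the effect.** A reader might take the 0.26 SD shift in the V1 mean as the damage. The ANOVA assesses change across visits, and the shared baseline shift removes much of it, or all of it at V2 when dropout follows the V1 level.
- **Direction for FSH is uncertain.** Pregnancy is recorded at V2, and a pregnant woman would have no usable basal FSH there. Missing values can therefore follow a good outcome as well.
- **The near-zero bias of the likelihood method is partly by construction.** Steps 3 and 4 place all dropout after V1, so the reason for leaving is always observed. Step 5 shows what happens otherwise.
- **FAS and PPS need not coincide.** A reader might infer that the two sets cannot check each other. Neither is defined, and a woman who deviates but attends every visit could be in one and not the other.
- **The V2 wording is not a clear contradiction.** For a woman who stops early, timing V2 from drug withdrawal could point to an earlier date than days 168–210. The day windows are already given, however, and one sentence would settle the matter.

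AMH, antral follicle count and ovarian haemodynamics are measured only at V0 and V1, so a missing V2 does not affect them.

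What remains is that the named method discards observed primary-endpoint data at a dropout rate the plan itself expects, while a method that keeps them is available in the same software.

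**Conclusion.** The concern holds as a conditional one and should be corrected. At the planned dropout, up to about 30 of 150 women would leave the FAS analysis of FSH and Kupperman score. The loss of information is certain for any woman with V1 but no V2.

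Bias in within-group change requires dropout related to response. On the stated assumptions it is modest, with the sizes shown in step 3, and it is most direct in the subclinical cohort. Bias in the randomised contrast further requires that dropout, or its link to response, differ between arms. In the examples tried it moved a −0.50 SD difference to between −0.48 and −0.43. The correlation, slopes and timing of loss are assumptions, not figures from the documents.

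**What to change.** **In the SAP**
- For FSH and Kupperman score, replace repeated-measures ANOVA with a linear mixed model (MIXED in SPSS): V0, V1 and V2 all as outcomes; arm, visit and arm-by-visit terms; unstructured covariance.
- Include all randomised women with any observed value, in the arm assigned, and define the FAS in those terms. A woman with only V0 then still contributes.
- Fit a separate model with visit as the only term for the subclinical cohort.
- Report dropout and reasons by arm.
- Add a simple missing-not-at-random sensitivity analysis, because the mixed model does not repair response-related loss before V1.
- Keep the PPS analysis as supportive.

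**In the protocol**
- State that women who stop the study drug are still asked to attend V1 (days 84–105) and V2 (days 168–210), counted from day 0.

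The cost is SAP wording, one protocol sentence, and slightly more analysis and follow-up effort. The software and the visits are already planned.

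### Bonferroni is valid for the pairwise comparisons, but for any family of exactly three means Shaffer-Holm keeps the same 5% family error, loses no rejection and adds some power

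*SAP*

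**What the plan says.** The SAP (Statistical analysis) covers measurement data in one sentence: "multiple time points were compared by repeated measures analysis of variance", and "pairwise comparisons were by Bonferroni test". It adds that "P<0.05 indicated that the difference was statistically significant". It does not state which pairs are meant, how many there are, at which visit they are tested, or whether tests are two-sided.

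The Protocol (Trial grouping and medication) has POI patients "randomly assigned to Kuntai group, control group and combination group according to 1:1:1", with 30 cases per arm. A further 30 subclinical patients form a self-controlled group that is not randomised. Under Treatment and follow-up, basal FSH, LH, E2 and the modified Kupperman score are measured at V0, V1 and V2. AMH, antral follicle count and ovarian blood flow are measured at V0 and V1 only. The primary endpoints are FSH and the modified Kupperman score. No effect size, SD or power is given.

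**The concern.** Bonferroni holds each of three pairs to 0.05/3 = 0.0167, whatever the other pairs show. With three means that is stricter than it needs to be. If one of the three equalities is false, at most one of the other two can be true, because two true equalities would force the third. Once one pair has been rejected, only one false rejection remains possible, and a test at the full 0.05 is enough to guard against it.

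The trial's purpose covers Kuntai alone and Kuntai combined with hormones, so more than one contrast is of interest. With 30 per arm and no stated power, power on the second and third contrasts is worth keeping when it can be had without extra patients.

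**Working it through.** **Inputs from the documents.** Three randomised arms, 30 per arm, alpha 0.05. The plan's only sample-size arithmetic reproduces: 4 × 30 = 120 completers, and 120/(1 − 0.20) = 150 enrolled. So 30 per arm is already the number after dropout.

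**Assumptions.** Two-sided tests, normal data, a common SD, one endpoint at one visit, and true differences in SD units over a range.

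**Rules.**
- Bonferroni: reject a pair if P ≤ 0.05/3 = 0.0167.
- Shaffer-Holm for three means: if the smallest P ≤ 0.0167, reject that pair and test the other two each at 0.05. Otherwise reject nothing.

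**Family error, by logic.**
- All three means equal: a false rejection needs the smallest P ≤ 0.0167, so the family error is the same as under Bonferroni and at most 3 × 0.0167 = 0.05.
- Exactly one equality true: only that pair can be falsely rejected, and this needs its P ≤ 0.05, so the error is at most 0.05.
- No equality true: no false rejection is possible.

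Any pair with P ≤ 0.0167 is rejected by both rules, so Shaffer-Holm loses none of Bonferroni's rejections. The argument does not need independent groups, so it also covers three visits within a group.

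**Bonferroni power by hand.** The noncentrality is d × √(n/2) = 0.7 × √15 = 2.71. The critical t at two-sided 0.0167 with 3 × 29 = 87 degrees of freedom is about 2.44. Power is about Φ(2.71 − 2.44) = Φ(0.27) = 0.61. At 0.8 SD, Φ(3.10 − 2.44) = Φ(0.66), or about 0.74.

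**Simulation** (30 per arm, pooled variance, 100,000 trials per setting):

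| True means (SD units) | Pair | Bonferroni | Shaffer-Holm | Gain (points) |
|---|---|---|---|---|
| 0, 0, 0.3 | each true pair | 0.11 | 0.13 | about 2 |
| 0, 0, 0.5 | each true pair | 0.31 | 0.37 | about 6 |
| 0, 0, 0.7 | each true pair | 0.61 | 0.69 | about 8 |
| 0, 0, 0.8 | each true pair | 0.74 | 0.82 | 7 to 8 |
| 0, 0, 1.0 | each true pair | 0.92 | 0.96 | about 4 |
| 0, 0.35, 0.7 | extreme pair | 0.61 | 0.63 | about 2 |
| 0, 0.35, 0.7 | each adjacent pair | 0.14 | 0.24 | about 10 |

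Other results:
- Family error under the full null is about 0.044 with either rule.
- With one arm differing, the false-rejection rate on the remaining null pair is about 0.017 under Bonferroni and rises to at most about 0.05 under Shaffer-Holm.
- The chance of rejecting at least one pair is the same under both rules, since both need the smallest P ≤ 0.0167.
- The chance of detecting both true differences at 0.7 SD rises from 0.45 to 0.61.
- No Bonferroni rejection was lost in any setting. Three paired visits gave the same error control.

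**The case against.** The strongest objection is that Bonferroni is simple, valid and comes with simultaneous intervals that match its decisions. That stands, and it is why this is an optional gain in efficiency.

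Second, error control is not costless. A null pair that remains after a true rejection is tested at up to 0.05 instead of 0.0167. The guarantee is per endpoint and visit. If the two primary endpoints were independent and each ran at 5%, the joint rate would be 1 − 0.95² = 9.75%. In the layout with one arm differing, Bonferroni would give about 1 − (1 − 0.0167)² = 3.3%. This also stands: the proposed rule does not deal with the two primary endpoints, and neither does the current SAP.

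Third, the Bonferroni clause directly follows the repeated-measures clause, so it may be meant for visit pairs. A replacement that spoke only of arms could then leave visit comparisons, and the whole subclinical group, without a rule. This stands and shapes the fix.

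Some stronger readings are tempting but not supported:
- A reader might expect 8 to 10 points of power from any stepwise rule. That range belongs to a different procedure, an overall F test at 0.05 followed by pairs at 0.05, with one arm differing by about 0.5 to 0.84 SD. Plain Holm gains only about 2 to 3 points in that layout.
- A reader might take 24 per arm as the analysable number (30 × 0.80). The Protocol plans 120 completers, so that would count dropout twice.
- A reader might infer that proportions will be compared by three unadjusted chi-square tests, with a family error near 12%. The SAP names only a chi-square test, and one overall three-arm test fits its wording equally well. The rule is unstated; unadjusted pairwise testing is not planned in the text.

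**Conclusion.** The point holds as a low-cost improvement. For exactly three means, Shaffer-Holm dominates Bonferroni at the same 5% family error per endpoint and visit. That part is logical and needs no assumed effect size.

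The size of the gain does rest on assumptions. It is about 6 to 8 points per true pair if one arm differs from two equal arms by 0.5 to 0.8 SD, about 2 points at 0.3 SD or for the extreme pair of evenly spaced means, and about 10 points for adjacent pairs 0.35 SD apart, where power is still only 0.24. At 0.7 SD, Bonferroni would need about 35 per arm to match Shaffer-Holm at 30 (35/30 = 1.17, or 17% more patients). The gain falls on the second and third contrasts and does nothing for the chance of a first rejection.

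A reader might conclude that the SAP's method is wrong or that the trial's conclusions are at risk. The documents do not support that, because Bonferroni controls the error it is meant to control.

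**What to change.** First decide which pairs the clause covers. Then replace it with text along these lines:

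> For each measurement endpoint, two kinds of family are defined. (a) The three comparisons between the randomised arms at a given visit form one family. (b) Where the endpoint is measured at V0, V1 and V2, the three visit comparisons within a group, including the self-controlled subclinical group, form one family. In each family the smallest two-sided P value is compared with 0.0167. If it is significant, the other two are each compared with 0.05; if not, no pair is declared different.

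Do not add the subclinical group to family (a). It is not randomised, and the step to 0.05 relies on there being exactly three means. AMH, antral follicle count and blood-flow parameters have only V0 and V1, so they have one within-group comparison and need no family (b).

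The cost is a short SAP edit made before the data are analysed. The rule works on ordinary pairwise P values, so it needs no new software, data or patients. Report Bonferroni intervals alongside the stepwise decisions, with a note that they may disagree. Say openly that control is per endpoint and visit and that a remaining null pair may be falsely rejected up to 5% of the time. State a separate rule for the two primary endpoints, and say how proportions will be compared across arms.

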| study endpoint | Primary endpoint : FSH, modified Kupperman score |
| | Secondary endpoints : |
| | (1) FSH/LH, LH, E ₂ ; (2) Antral follicle count (AFC); (3) Anti- Müllerian hormone (AMH); (4) |
| | Proportion of patients with normal menstruation; (5) Ovarian hemodynamics parameters (PSV, |
| | EDV, S/D, RI and PI); (6) Clinical pregnancy rate (patients with reproductive needs). |
| security | 1 Blood routine (RBC, WBC, PLT, HGB), liver function (ALT, AST) and renal function (BUN, |
| indicators | Cr); |
| | 2 Patient adverse events were recorded. |

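### The SAP names no paired test for before-after proportions, so an ordinary chi-square on normal menstruation in the subclinical cohort would be too conservative and could miss a real change

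*SAP*

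**What the plan says.** The SAP's Statistical analysis section is one paragraph. For count data it states that "enumeration data were expressed by the number of cases or percentages" and then gives chi-square as the test. It names no paired or exact alternative and does not separate comparisons between groups from comparisons over time. The significance rule is "P<0.05 indicated that the difference was statistically significant".

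In the Protocol, under Trial grouping and medication (item 2), the subclinical patients form a single "self-control before and after experiment group (30 cases" and have no control arm. The secondary endpoints include "Proportion of patients with normal menstruation". The inclusion criteria admit women "with or without oligomenorrhea or" menopause, so menstrual status may be mixed at entry.

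For measurement data the same SAP paragraph specifies repeated measures analysis of variance with Bonferroni pairwise comparisons. The two primary endpoints, FSH and the modified Kupperman score, fall under that rule.

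**The concern.** The ordinary 2x2 chi-square compares two independent groups. In the subclinical cohort the before and after proportions come from the same women. A woman's menstrual status at one visit is likely to resemble her status at another, so the before-after difference varies less than independence implies. The chi-square then uses too large a standard error, and the P value and any interval built the same way are too cautious.

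A real improvement in menstruation could therefore be reported as not significant in a cohort that has no other comparison to fall back on. The SAP provides for the repeated measurement of continuous data but has no counterpart for proportions.

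**Working it through.** **1. The plan's own figure.** The only derived number in the documents is enrolment. The Protocol says "It is planned to complete 120 cases" and "considering the 20% dropout rate, at least 150 cases need to be" enrolled: 120 / (1 − 0.20) = 150, which reproduces. The 120 completers are 3 × 30 randomised plus 30 subclinical. The subclinical share of enrolment is 30 / 0.80 = 37.5, or about 38. No power, effect size or proportion is stated for any endpoint.

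**2. Inputs.**
- From the documents: n = 30 pairs (the planned completers) and a 0.05 significance level.
- Assumed: a two-sided test; 50% normal menstruation at both times for alpha; 50% rising to 75% for power; phi of 0.2, 0.3 and 0.5.

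**3. Why pairing matters.** With the same proportion p at both times, the true variance of the before-after difference is 2p(1 − p)(1 − phi)/n. The ordinary chi-square uses 2p(1 − p)/n. Its actual two-sided alpha is therefore about 2 × [1 − Φ(1.96 / √(1 − phi))]:
- phi 0.2: 1.96 / 0.894 = 2.19, alpha about 2.8%
- phi 0.3: 1.96 / 0.837 = 2.34, alpha about 1.9%
- phi 0.5: 1.96 / 0.707 = 2.77, alpha about 0.6%

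**4. Exact alpha.** Summing the multinomial probabilities of every paired table with n = 30, at 50% before and after:

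| phi | ordinary chi-square | exact McNemar | mid-P McNemar | asymptotic McNemar |
|---|---|---|---|---|
| 0.2 | 3.0% | 2.4% | 4.3% | 4.3% |
| 0.3 | 2.0% | 2.3% | 4.2% | 4.3% |
| 0.5 | 0.6% | 1.8% | 3.7% | 4.5% |

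At phi 0 the ordinary chi-square has an alpha of 5.2%. It exceeds nominal materially only if the correlation is negative (7.6% at −0.2).

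**5. Exact power**, same method, 50% rising to 75%:

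| phi | ordinary chi-square | exact McNemar | mid-P McNemar | asymptotic McNemar |
|---|---|---|---|---|
| 0.2 | 52% | 48% | 58% | 58% |
| 0.3 | 52% | 54% | 64% | 64% |
| 0.5 | 52% | 70% | 81% | 83% |

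Mid-P gains about 6, 12 and 29 points over the ordinary chi-square. Exact McNemar loses about 4, then gains about 2 and 19.

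**6. How high can phi go?** For 50% and 75%, the proportion normal at both times cannot exceed 0.50. The largest covariance is 0.50 − 0.50 × 0.75 = 0.125, so the largest phi is 0.125 / √(0.25 × 0.1875) = 0.58. At phi 0.5 only about 2% of women would go from normal to abnormal menstruation, so that row is close to the extreme.

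**7. Which endpoints are touched.** FSH and the Kupperman score are continuous and analysed by repeated measures. Pregnancy is recorded at V2 only, so it has no before value. Among the efficacy endpoints, that leaves normal menstruation.

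**The case against.** The strongest reply is that the SAP says only chi-square, not Pearson or unpaired, and McNemar's test is also referred to a chi-square distribution. That stands as an ambiguity: the documents do not show that the sponsor will run the wrong test. But the two tests give different answers on the same data, and a plan that permits either has not fixed the analysis.

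A second reply is that the before-after test of menstruation is itself inferred. The Protocol's visit list schedules no menstrual assessment, and subclinical POI is defined there by FSH of 15 to 25 IU/L alone. If most of these women menstruate normally at entry, there is little to test. This also stands, and is why the visits need naming. It does not remove the point, because the endpoint is listed and this cohort has no other comparison.

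A reader might infer that the plan gives up much of its power whatever the data look like. The documents give no correlation, and the calculation does not support that: at phi 0.2 the loss against mid-P is about 6 points, and exact McNemar does worse than the ordinary chi-square. A reader might also infer a risk of false positives. With the positive correlation to be expected, the error runs the other way.

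**Conclusion.** The point holds in a limited form. The SAP does not specify a test suited to paired proportions, and the one test it names, read in its ordinary sense, has the wrong error rate for the subclinical cohort whenever phi is not zero. With positive phi the actual alpha falls to between 3.0% and 0.6% over phi 0.2 to 0.5. The power cost ranges from small at phi 0.2 to large at about 0.5.

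These sizes rest on assumed proportions, an assumed phi, a two-sided test and n = 30. The full analysis set could approach 38, which would change the figures but not the mismatch.

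The scope is one secondary endpoint in one cohort, plus any before-after count comparison made elsewhere; none is stated for the randomised arms. It would be wrong to read this as a threat to the primary results: repeated measures ANOVA already takes account of the same women being measured over time. The change should be made, but the trial's main conclusions do not depend on it.

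**What to change.** Add to the SAP that proportions compared before and after in the same women are tested by McNemar's test, mid-P (or asymptotic), for two visits and by Cochran's Q for three, and are reported as a paired difference with a 95% CI. Name the visits at which menstrual status is recorded. Keep chi-square for comparisons between the randomised arms.

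The cost is a sentence or two in the SAP, with no extra patients and no design change. Mid-P is itself mildly conservative here (alpha about 3.7% to 4.3% over phi 0.2 to 0.5). The exact version is not preferred: its alpha is only about 2%, and at low phi it offers little or no gain in power over the ordinary chi-square.
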